### **Secondary Endpoints**

- Pain level following the injection based on Visual Analog Scale scoring. [Time Frame: 6 months]

Pain will be measured by the Visual Analog Scale for pain (VAS Pain). This will consist of a comparison of mean values for VAS scoring scales pre-injection and at the 6 month follow-up assessment. Clinically significant outcomes will be determined based on the minimal clinically important difference (MCID) occurring for each respective scale, which is defined as the smallest change score needed for the effect to be considered clinically relevant; described below. Specifically, VAS represents a patient-reported measurement tool used to quantify perceived level of pain, graded on a scale from 0 to 10 with 0 representing no pain and 10 representing the worse pain possible, and with precise measurement of the marked pain level's distance from 0 comprising the pain level.

- Functional outcomes scoring using Single Assessment Numerical Evaluation (SANE), PROMIS Physical Function CAT (PF CAT), and Knee Injury and Osteoarthritis Outcome Score (KOOS) scoring scales. [Time Frame: 6 months]

Functional outcomes will be evaluated throughout the study period. The SANE asks the patient to evaluate their percentage of normal on the affected joint or region of interest. This is a one-question survey with a scale from 0-100%. The PFCAT is a bank of questions related to physical function. It is a computerized adaptive test that asks the patient to self-report capabilities rather than actual performance of physical activities. It includes functioning of upper extremities, lower extremities, and central regions and also assess instrumental activities of daily living, such as running errands. The KOOS is a survey that assesses joint symptoms, pain, pain during daily activities, physical function in daily living, as well as physical function during sports or

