**Exploratory Endpoints**

- Number of treatment emergent adverse events (AEs) directly related to the injection. [Time Frame: 1 day, 2 days, 1 month, 3 months, 6 months and 12 months]
- Pain level following the injection based on Visual Analog Scale scoring. [Time Frames: 1, 3, 6 and 12 months]
- Functional outcomes scoring using Single Assessment Numerical Evaluation (SANE), PROMIS Physical Function CAT (PF CAT), and Knee Injury and Osteoarthritis Outcome Score (KOOS) scoring scales. [Time Frames: 1, 3, 6 and 12 months]

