**A Phase I/II Randomized, Double-Blinded Standard of Care (Corticosteroid vs Sterile Amniotic Fluid for Osteoarthritis**

**PI: [name].**

**Version: 5.00 dated 23MAY2023**

At the end of 12 months, the pain and outcomes assessments for both treatment arms will be compared and assessed using the Visual Analog Scale (VAS), Single Assessment Numerical Evaluation (SANE), PROMIS Physical Function CAT (PF CAT), and Knee Injury and Osteoarthritis Outcome Score (KOOS).

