**DATA ANALYSIS**

The primary endpoint (need for a repeat injection) will be compared between the two arms using Fisher's Exact test. An alpha 0.05 will be used as the threshold for statistical significance. Missing data will remain missing rather than be imputed since this is a pilot study assessing preliminary safety and feasibility.

The secondary endpoint (pain) will consist of a comparison of mean values for VAS scoring scales pre-injection and at follow-up visits at 1, 3, 6 and 12-months. Clinically significant outcomes will be determined based on the minimal clinically important difference (MCID) occurring for each respective scale, which is defined as the smallest change score needed for the effect to be considered clinically relevant.

Continuous secondary and exploratory endpoints will be compared between arms using Wilcoxon Rank Sum tests. Categorical endpoints (including safety outcomes) will be compared between arms using Chi-squared tests. In cases of small counts, exact tests may be used.

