**SAMPLE SIZE CALCULATIONS AND STATISTICAL POWER**

The primary endpoint is the need for a repeat injection. Based on historic data, about 50% of individuals who receive a steroid injection return for an additional injection within six months due to pain. Assuming a significance level of 0.05 and a need for a repeat injection in the AF arm of 10%, with 60 total patients (30 per arm), we have about 90% power to detect a difference in need for repeat injections at 6 months between the two arms. Expecting approximately 5 randomizations per week, 60 patients will take approximately 3 months to enroll.

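### Secondary pain and function lack one fixed time point and one defined between-arm comparison, and the collected baseline scores are not used as a covariate

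*Combined protocol and SAP*

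**What the plan says.** **Test.** Data Analysis states: "Continuous secondary and exploratory endpoints will be compared between arms using Wilcoxon Rank Sum tests". It names no covariate, no repeated-measures model and no effect estimate, and it does not choose between follow-up score and change score. The minimal clinically important difference is defined on a change score, but no value is given for any scale.

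**Secondary pain.** The Secondary Endpoints section gives month 6: "This will consist of a comparison of mean values for VAS scoring scales pre-injection and at the 6 month follow-up assessment". Data Analysis, also calling pain the secondary endpoint, gives a "comparison of mean values for VAS scoring scales pre-injection and at follow-up visits at 1, 3, 6 and 12-months".

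**Secondary function (SANE, PF CAT, KOOS).** The Secondary Endpoints section heads these with a 6-month time frame, then ends by listing months 1, 3, 6 and 12.

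**Other places.** The Exploratory Endpoints section lists "Pain level following the injection based on Visual Analog Scale scoring. [Time Frames: 1, 3, 6 and 12 months" and the same four visits for function, so month 6 is both secondary and exploratory. The end of Data Collection says: "At the end of 12 months, the pain and outcomes assessments for both treatment arms will be compared".

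**Baseline.** The Screening and Enrollment section and the Patient Study Calendar collect VAS, SANE, PF CAT and KOOS at baseline. Entry requires typical pain of at least 4 out of 10.

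**Threshold.** The only one in the plan is given in the paragraph on the primary endpoint: "An alpha 0.05 will be used as the threshold for statistical significance".

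**The concern.** Pain relative to corticosteroid is a stated secondary objective, so the plan should fix what will be compared, when and how. Three things are open.

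1. A pre-injection versus follow-up comparison of means is, read literally, a contrast within an arm. The between-arm test named afterwards is a rank test, which does not compare means and yields no stated difference or interval. Two analysts could follow this text and report different results.
2. Depending on the section, secondary pain is one visit or four. With four, and no rule for choosing among them, the false-positive risk for pain exceeds the nominal level.
3. With 30 patients per arm, precision is scarce. The baseline scores are available but are not planned as covariates.

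**Working it through.** **1. The plan's own power figure.** The sample size section says "with 60 total patients (30 per arm), we have about 90% power to detect a difference", for 50% versus 10% repeat injection. Exact enumeration of the two-sided Fisher test at 30 per arm gives 91.4%, so the figure reproduces. It concerns the primary endpoint only. The documents give no SD, target difference, correlation or power for pain or function, so the inputs in steps 2 to 5 are assumptions, apart from 30 per arm, the 0.05 threshold (taken as two-sided) and the entry rule.

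**2. Four visits at 0.05.** Four independent tests would give 1 − 0.95⁴ = 18.5%. With equally correlated normal test statistics, the chance of at least one two-sided p < 0.05 under no effect is about 17% at between-visit correlation 0.3 and about 11% at 0.8.

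**3. Gain from baseline adjustment, unrestricted baseline.** Let n = 30 per arm, d = difference/SD, and ρ = baseline to follow-up correlation. The noncentrality parameters are:

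- Wilcoxon on the follow-up score: d·√(n/2 · 3/π)
- Wilcoxon on change: the same, with d divided by √(2(1−ρ))
- ANCOVA: d/√(1−ρ²) · √(n/2), on 57 df

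A 1.5-point difference with SD 2 is d = 0.75; the closed form was run at d = 0.74. At ρ = 0.5 the follow-up-score Wilcoxon has 0.74 × √(15 × 0.955) = 2.80, giving 78.6% power. ANCOVA has (0.74/0.866) × √15 = 3.31, giving 90.2%.

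| ρ | Wilcoxon, follow-up | Wilcoxon, change | ANCOVA | Gain over follow-up | Gain over change |
|---|---|---|---|---|---|
| 0.3 | 78.6% | 64.3% | 84.0% | 5 | 20 |
| 0.5 | 78.6% | 78.6% | 90.2% | 12 | 12 |
| 0.7 | 78.6% | 94.5% | 97.6% | 19 | 3 |

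Simulation agrees to within about a point or two. The gain also depends on d. Over the follow-up-score Wilcoxon at ρ = 0.5 it is 13 points at d = 0.5, 6 at d = 0.3 and 3 at d = 1.0.

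**4. The same case with the entry rule.** Baseline VAS is now truncated to 4–10, with an assumed underlying mean of 5 or 6. An underlying correlation of 0.5 falls to about 0.35–0.38 among those enrolled, and follow-up scores also become less variable. The follow-up-score Wilcoxon therefore improves while ANCOVA barely moves: at underlying ρ = 0.5, 0.84–0.85 against 0.90–0.91.

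| Underlying ρ | Gain over follow-up-score Wilcoxon | Gain over change-score Wilcoxon |
|---|---|---|
| 0.3 | about 3 | about 11 |
| 0.5 | about 6 | about 7 |
| 0.7 | about 8 | about 2 |

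These move by about a point with the assumed mean and simulation error. How the restriction is modelled matters more: clipping scores to 0–10 with baseline at least 4 leaves a gain of 11 points at d = 0.74, ρ = 0.5. The entry rule acts directly on VAS only, so step 3 is the nearer guide for SANE, PF CAT and KOOS.

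**5. Regression to the mean.** For a normal baseline with mean μ and SD σ, the expected fall is (1−r)·σ·φ(a)/(1−Φ(a)), with a = (4−μ)/σ. The smallest case (μ = 6, σ = 2, r = 0.6) is 0.4 × 2 × 0.242/0.841 = 0.23 points. The largest (μ = 5, σ = 2.5, r = 0.5) is 0.5 × 2.5 × 0.368/0.655 = 0.70 points. It is expected equally in both arms.

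**The case against.** An unadjusted rank test is valid for small samples and bounded scales, and these are secondary and exploratory endpoints in what Data Analysis calls a pilot. That stands: preferring ANCOVA is a matter of efficiency and clarity, and the planned test is not invalid.

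Several stronger readings are tempting, and the documents do not support them.

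- *The plan loses ten or more points of power.* All the inputs are assumed, and the gain can be as small as 2 or 3 points. Against a follow-up-score Wilcoxon, ten points needs a correlation near 0.5 or more and a moderate effect.
- *The baseline is wasted.* The clinically important difference is defined on change, so baseline may enter by subtraction. What can be said is that the choice is unstated and no covariate is planned.
- *The trial will claim efficacy from pre/post means.* Regression to the mean would undermine such a claim, but the documents never make it. Randomization balances that fall between arms and a between-arm test is specified. The pre/post wording also covers pain only.
- *Month 12 is a third competing endpoint.* The Data Collection sentence can be read as saying when the comparison is made. Listing the full visit series as exploratory is a common layout. The firm conflict for pain is between the Secondary Endpoints section and Data Analysis.

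Two limits of the remedy also stand. Fixing month 6 still leaves at least four scales tested, several domains within KOOS, and no multiplicity rule. Rescue steroid injection is allowed at any time, and the sample size section assumes "about 50% of individuals who receive a steroid injection return for an additional injection within six months due to pain" against 10% in the pAF arm. A month-6 score therefore mixes assigned treatment with unequal rescue, whichever test is used.

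**Conclusion.** The point holds as one of specification, with a modest efficiency gain attached. The plan gives two answers on when secondary pain is assessed, leaves the form of the outcome open, describes pain by a within-arm contrast, and plans no adjustment for baseline scores it collects.

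If all four visits were tested, the false-positive chance for pain would be about 11 to 17%. This rests on the assumed between-visit correlations and on applying the plan's 0.05 threshold to each visit. The power gain, for an assumed 1.5-point difference, SD 2 and correlation 0.3 to 0.7, is about 5 to 19 points over a follow-up-score Wilcoxon with an unrestricted baseline, and about 3 to 8 with baseline VAS truncated at 4. Against a change-score Wilcoxon with that truncation it is about 11, 7 and 2 points at correlations 0.3, 0.5 and 0.7. A reader might infer that the trial's main comparison is weakened; it is not, because primary power does not depend on any of this.

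**What to change.** In Data Analysis:

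- Make the between-arm difference at month 6, adjusted for the baseline score of the same scale and reported with a 95% CI, the secondary analysis for VAS, SANE, PF CAT and KOOS. Use ANCOVA, or a repeated-measures model with baseline and arm-by-visit terms.
- Keep the Wilcoxon as a sensitivity analysis and state whether it uses follow-up or change scores.
- Label months 1, 3 and 12 exploratory, and report pre/post means descriptively only.
- Describe the month-6 difference as including the effect of any rescue injections received by then.
- Say that the several month-6 scale results carry no multiplicity control, unless an order is set.

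Then align the Secondary Endpoints, Exploratory Endpoints, Data Collection and Data Analysis sections to this. In particular, list month 6 once, as secondary, and say whether the Data Collection sentence means the timing of the analysis.

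The cost is wording only: no added visits, measurements or patients, since the baseline and follow-up scores are already scheduled. The adjusted model adds a linearity assumption, which the retained Wilcoxon helps to check.

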**STUDY SUMMARY**

This study will look at blinded standard of care (SOC) steroid injection vs. amniotic fluid injection (pAF) to treat and reduce osteoarthritis (OA) inflammation and pain. The main objectives of this study are to establish the safety and tolerability of allogeneic intra-articular pAF injections. Secondary objectives include pain levels and functional outcome scoring in patients over a 12 month time frame.

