**Randomization**

Consented patients will be randomized into two groups at a 1:1 ratio using block permutations of 2 and 4. Randomization will be done using either an online randomization service or envelope system. Randomization will occur following the patient's consent into the study, either at the initial visit or the day of the planned injection. Once the randomization number is obtained, unblinded research staff will prepare the appropriate study drug. The injections will be blinded to the research coordinator in charge of data entry, the treating physician and the patient. Clinical staff will prepare the study drug injection and maintain the blind by placing a blank label over the syringe to ensure that the treatment is blinded to the patient and treating physician. Once a patient has been randomized, they become an enrolled subject and will be included in the intention to treat analysis of the trial outcomes, regardless of whether or not they receive study drug.

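### Safety is a primary objective, but its final statistical analysis is only a between-arm test with an open choice between chi-squared and exact, and no estimate with a confidence interval is planned

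*Combined protocol and SAP*

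**What the plan says.** The Synopsis lists the safety of pAF as the first primary objective, and the Study Summary says: "The main objectives of this study are to establish the safety and tolerability of allogeneic intra-articular pAF injections". The Exploratory Endpoints section, by contrast, places injection-related adverse events among the exploratory endpoints, worded as a number of events.

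The Data Analysis section covers the final analysis of categorical safety data in two sentences: "Categorical endpoints (including safety outcomes) will be compared between arms using Chi-squared tests", then "In cases of small counts, exact tests may be used". It does not define small counts. It plans no per-arm rate with a confidence interval, no risk difference, no margin and no statement of the precision that 30 pAF participants provide. The same section fixes Fisher's exact test for the primary endpoint and adds "An alpha 0.05 will be used as the threshold for statistical significance".

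The sample size section gives power for repeat injection only: "with 60 total patients (30 per arm), we have about 90% power to detect a difference in need for repeat injections at 6 months". The adverse event section lists expected events without frequencies.

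**The concern.** The objective asks how often pAF causes harm. A test of no difference from steroid does not answer that. It compares pAF with an injection that has reactions of its own, and with 30 per arm it will often miss a real excess of an uncommon event. Without an interval, a reader who sees a non-significant P value cannot tell a reassuring result from an uninformative one.

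The second problem is the open choice of test. Adverse event counts in a 60-patient trial are likely to be small, which is where chi-squared and exact tests part company. If the choice is made after the counts are known, the reported significance of a safety difference can depend on it.

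**Working it through.** **Inputs from the documents.** 30 per arm and 1:1 allocation (sample size and Randomization sections); alpha 0.05 (Data Analysis); chi-squared as the default for safety with exact tests optional (Data Analysis).

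**Assumptions.** Tests are two-sided, as sidedness is not stated. The 0.05 threshold also applies to safety, although its sentence follows the primary endpoint. All 30 per arm are evaluable. Adverse event rates are my assumptions, because the documents give none.

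**Method.** For true rates p1 (steroid) and p2 (pAF), power is the sum of Bin(a; 30, p1) × Bin(b; 30, p2) over all 31 × 31 tables (a, b) in which the test gives P ≤ 0.05. Chi-squared is uncorrected.

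**Check against the plan's own figure.** The plan assumes that "about 50% of individuals who receive a steroid injection return for an additional injection within six months due to pain", against 10% with pAF. The enumeration gives 91.4% with Fisher's exact test and 94.9% with chi-squared. The stated 90% or so is reproduced.

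**Power for safety under assumed rates.**

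| Steroid vs pAF | Fisher | Chi-squared | Chi-squared significant, Fisher not |
|---|---|---|---|
| 2% vs 10% | 4.3% | 21.8% | 17.5% |
| 5% vs 15% | 9.3% | 26.4% | 17.0% |
| 3% vs 15% | 14.7% | 39.2% | 24.5% |
| 5% vs 20% | 24.1% | 45.3% | 21.2% |
| 10% vs 30% | 37.2% | 49.9% | 12.8% |

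The results depend heavily on the assumed rates. Threefold and fivefold excesses over steroid rates of 1% to 10% give Fisher power from about 0% (1% vs 3%) to 91.4% (10% vs 50%), and chi-squared power from 0.9% to 94.9% for the same two pairs.

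**Single tables, 30 per arm.**

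- 0 vs 4 events: chi-squared = 60 × (30 × 4)² / (30 × 30 × 4 × 56) = 4.29, P = 0.038. Fisher P = 2 × C(30,4)/C(60,4) = 2 × 27,405/487,635 = 0.112.
- 0 vs 5 events: chi-squared = 60 × (30 × 5)² / (30 × 30 × 5 × 55) = 5.45, P = 0.020. Fisher P = 2 × C(30,5)/C(60,5) = 2 × 142,506/5,461,512 = 0.052.
- 1 vs 6 events: chi-squared P = 0.044, Fisher P = 0.103.

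With no events on steroid, chi-squared is significant from 4 pAF events and Fisher from 6.

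**Error rate.** Over common true rates of 1% to 50%, the largest false-positive rate is 2.7% for Fisher and 5.5% for chi-squared. Fisher is the conservative test, and its lower power is the price.

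**Precision with no events.** The Clopper-Pearson upper limit for 0/30 (two-sided 95%) is 1 − 0.025^(1/30) = 11.6%.

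**The case against.** The strongest reply is that safety in this trial does not rest on these tests. The Study Stopping/Discontinuation section halts the study on events that need no comparison between arms. The Study Enrollment Staggering section requires DSMB review of the first six subjects. The monitoring sections provide medical monitor review of serious events and an unblinded DSMB that can suspend enrollment. This stands: a reader might infer that safety is judged solely by significance tests, and for the trial as a whole that is untrue. But these provisions govern whether the trial continues. They do not say how the final safety results will be estimated or reported.

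A reader might also infer that a non-significant P value will be declared proof of safety. No section says so, and Data Analysis calls the trial a pilot with preliminary safety aims. The gap is that the final analysis offers nothing better to rest a conclusion on. Nor can it be said that the pAF event rate will go unseen, since any comparison needs per-arm counts and the DSMB receives an adverse event summary. What is missing is the interval.

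On the numbers, it is tempting to quote Fisher's 15% and 37% (3% vs 15%, 10% vs 30%) as the plan's power for three- to fivefold excesses. That is not supportable. The rates are assumed, other pairs in that fold range give anything from about 0% to 91%, and the plan's default chi-squared gives 39% and 50% for the same two pairs.

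Finally, prescribing Fisher for safety would reduce sensitivity to harm: at 3% vs 15%, power falls from 39% to 15%. That is a fair objection to treating a fixed test as the whole remedy.

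**Conclusion.** The point holds for the final statistical analysis of categorical safety outcomes. For a primary objective, the plan offers a difference test, an undefined rule for switching tests, and no interval or precision statement. At each of the five assumed rate pairs tabulated, the excess is missed at least half the time whichever test is used (power 4% to 37% with Fisher, 22% to 50% with chi-squared). The two tests disagree in about 13 to 25% of trials at those rates. The power and disagreement figures rest on assumed event rates, two-sided 0.05 and a full 30 per arm. The single-table P values need only the 30 per arm, and the 11.6% limit needs only 30 evaluable pAF participants. This should be changed, but it is a defect of analysis and reporting. It does not show that safety oversight during the trial is inadequate.

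**What to change.** In the Data Analysis section, make estimation the safety analysis:

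- For each safety outcome, report the number and percentage of participants affected in each arm with Clopper-Pearson 95% confidence intervals. Count participants, because these intervals do not apply to a total number of events.
- Report the risk difference (pAF minus steroid) with an exact or score 95% confidence interval, naming the method.
- State that zero events among 30 pAF participants excludes only rates above about 11.6% (two-sided exact 95%), and that a non-significant difference is not evidence of safety.
- If P values are kept, name one test in advance for all categorical safety outcomes and call it descriptive. Fisher's exact test matches the primary endpoint and holds the error rate, but it is less sensitive to harm than chi-squared. That is a further reason to rest the conclusion on the intervals.

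The cost is a few sentences, a few more table columns and a visibly more modest safety claim. Sample size and trial conduct do not change.
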